The Data Safety Monitoring Committee (DSMC) concluded on 10/25/19 that progression of myopia is occurring more frequently in subjects treated with overminus spectacles compared to non-overminus spectacles. Between baseline and 12 months, the mean change in spherical equivalent refractive error at 12 months was -0.42 D (diopter) in the overminus group and -0.05 D in the non-overminus group (difference = 0.39 D P = <.0001). The proportion of subjects whose spherical equivalent refractive error changed by more than 1.00D was 17% in the overminus group (29 of 168); and 2% in the non-overminus group (3 of 146). The DSMC recommended that all subjects active in the full treatment* or weaning phases in both treatment groups be asked to come in for a visit as soon as possible to be given the new information, complete their pending follow-up visit, receive study-paid non-overminus glasses (regular

glasses or no-correction glasses) to be worn through 18 months, and be invited to continue in the study after 18 months to be treated at investigator discretion and to return for visits at 24 and 36 months.

82 83 84

85

86

87

80

81

*Note that the protocol does not require amending the 0 to 12-month on-treatment period in order to discontinue full overminus treatment given that the 37 remaining 12-month visits (as of 11/5/19) were planned to occur by December 2019. These 12-month visits will be completed only slightly early (all subjects have ≥9 months of treatment). As detailed above, non-overminus glasses will be prescribed between 12 and 18 months.

88 89 90

Protocol Change #2

91 92

Original Protocol

93 94 A lens change was required at the 15-month visit in both treatment groups to allow for discontinuation of half-strength (-1.25D) overminus spectacles in the overminus group. The 15-month glasses prescription is the same as the non-overminus group has received throughout the protocol.

95 96 97

Changed Protocol

98 99 100

The 15-month spectacle prescription is the same as in the original protocol (i.e., non-overminus for both treatment groups), but whether a patient needs to receive a change in spectacles at 15 months to achieve this prescription depends on whether their spectacles had been changed to non-overminus at the 12-month visits occurring after Protocol Amendment II.

101 102 103

Section 2.6.1 on treatment in the **overminus** group has been revised as follows:

104

108

109

110

111

112

15-Month*

105 106 107

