 - 10. Assessment of Deviation Throughout Exam (Masked)

1407 1408

The following procedures should be performed by either the Masked Examiner or another study-certified examiner:

14101411

1409

1412

1413

1414

1417

14181419

1420

1421

1422

1423

1424

- 11. Distance Visual Acuity Testing: Monocular distance visual acuity testing with the habitual correction and without cycloplegia will be measured using the same testing procedure as used for enrollment. Visual acuity may be tested at the start of the exam or before the cycloplegic refraction.
- 1415 12. Cycloplegic Autorefraction (12-month and 18-month visits only, mandatory if autorefractor is available at the site)
 - Refractive error must be measured with the same autorefractor used at enrollment following cycloplegia with 1% cyclopentolate (see cycloplegic refraction below).
 - If cycloplegic autorefraction was completed at enrollment, then it must be measured with the same autorefractor used at enrollment.
 - Regardless of whether cycloplegic autorefraction was completed at enrollment, it is mandatory to measure cycloplegic autorefraction if an autorefractor is available at the site.
 - Recorded values will be based on a single measurement by the instrument (which may be a mean of several individual measures depending on system)
- 1426 13. Cycloplegic Axial Length Measurement and Additional Biometry (18-month visit only) (see manual of procedures).

• Axial length

1433 1434

1435

1436

14371438

1439

14401441

1442

1443

1444

1445

1446

1447 1448

1449 1450

1451

14521453

1454

1455

1456

14571458

1459

1460

1461

1462

1463 1464

1465

1466

1467 1468 1469

1471

- Flat corneal radius
- Anterior Chamber depth
- Lens thickness, if available
- 1432 14. Cycloplegic Refraction (12-month and 18-month visits)
 - A cycloplegic refraction will be performed at the 12-month and 18-month visits. The cycloplegic refraction will be performed regardless of whether a cycloplegic autorefraction is performed.
 - Cycloplegic refraction is performed 30 to 45 minutes following at least one application of cyclopentolate 1% per investigator's usual dosage and timing routine.
 - The cycloplegic refraction is based on cycloplegic retinoscopy, which may be done with glasses off or as an over-refraction in front of the current spectacles. Subjective refraction is allowed.

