191 no statistical testing. The analyses involving 12-month data will be conducted using
192 available 12-month outcome data in accordance with the specifications laid out in this
193 SAP.
194

195 **2.1.9. Multiple Imputation of Missing Values**

196 The multiple imputation will be performed for missing data using Monte Carlo Markov
197 Chain (MCMC) modeling, which includes the mean distance control scores at all follow-
198 up visits prior to and including the 12-month visit, and the following baseline factors:
199 distance PACT, age, and refractive error. The mean distance control score will be used in
200 the MCMC model when multiple baseline measurements are available. The multiple
201 imputation will be performed separately by treatment group to account for potential
202 interaction between the treatment groups and the follow-up distance control scores. The
203 number of imputations will be set to 100. For the participants who started IXT treatment
204 other than overminus or non-overminus spectacles, only data from the visits prior to
205 starting such treatment will be used in the MCMC model. Missing baseline data are not
206 expected for distance PACT, age, and refractive error; however, if such missing data

207 occurs, it will be imputed in the MCMC model so that participants with such missing
208 baseline data are included in the analysis.

209

210 If the study is not terminated early based on partial or complete 12-month data (as
211 specified in Section 2.3), the missing mean distance control scores at all follow-up visits
212 (including 15-month and 18-month visits) will be imputed again using an MCMC model
213 that includes mean distance control scores at all follow-up visits prior to and including
214 the 18-month visit, following the same principles specified above for the imputation of
215 primary outcome at 12 months. Both the primary analysis for the 12-month outcome
216 specified in Section 2 (including sensitivity analyses) and the secondary analysis for the
217 18-month outcome outlined in this SAP will be conducted using this newly imputed
218 dataset and the results will be used in the final manuscript.

219

220

221 **2.2 Secondary Analysis: Efficacy of Overminus After Treatment Discontinuation** 222 **(18 Months, Off-Treatment)**

223

224 The analyses specified in the secondary analysis will be performed on the full cohort
225 which includes participants who were and were not prescribed full treatment between 0 to

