459 spherical equivalent refractive error will be performed using an ANCOVA model which
460 adjusts for baseline refractive error and baseline age. The latter was added as a post-hoc
461 adjustment factor, as age is expected to be associated with refractive error at the 12-
462 month (and 18-month) time points. The treatment group difference, 95% confidence
463 interval, and p-value will be calculated. This analysis will be done combining refractive
464 error obtained by subjective refraction or retinoscopy and separately from refractive error
465 obtained by autorefraction.

466

467 **4.1.10 Quality of Life**

468 At both the 12-month and 18-month time points, a two-sided treatment group comparison
469 of the child, and each of the three parent scales in the IXTQ HRQOL (Quality of Life)
470 will be performed each using the Wilcoxon Rank Sum Test as it is expected that scores
471 will not be normally distributed and will have a substantial ceiling effect. The treatment
472 group difference, 95% confidence interval, and p value will be calculated for both the
473 Rasch-scored data¹ and for 0 to 100-scaled data. The reported p-value will be derived
474 from the analysis of Rasch-scaled data, while to aid in interpretation, the 0 to 100-scaled
475 data will be used when reporting the median values for each treatment group.

476

¹ Leske DA, Holmes JM, Melia M, on behalf of Pediatric Eye Disease Investigator Group. Evaluation of the Intermittent Exotropia Questionnaire using Rasch analysis. JAMA Ophthalmol 2015;133:461-5.

477 A potential secondary manuscript, to be detailed in a separate SAP, will describe quality
478 of life, IXT symptoms, and spectacle wear issues, the relationships among these, and
479 relationships between these and clinical measures.

480

481 **4.1.11 IXT Symptom Survey**

482 A 7-item survey of IXT-related symptoms will be completed by the child at the
483 enrollment, 6-month, 12-month, and 18-month outcome exams. For each IXT-specific
484 symptom, the child is asked how often it occurs, using the response choices of “never”

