576 Of the 355 expected 18-month visits (as of 11/5/19), approximately 283 participants
577 (80%) will have completed a full 3-months of prescribed weaning before discontinuing
578 overminus (or non-overminus); approximately 35 to 54 (20% to 25%) participants will
579 have completed partial weaning, and approximately 18 to 37 participants (5% to 10%) are
580 expected to have no weaning at all per Protocol Amendment II. The summary statistics
581 for distribution of 18-month distance control and change from baseline in distance control
582 will be tabulated according to treatment group and whether full, partial, or no prescribed
583 weaning.

584

585 **4.2.3 Participants with Baseline Control of 3 to 5 Points (Spontaneous Tropia)**

586 Participants with baseline distance control of 3 to 5 points may have a better likelihood of
587 improving ≥ 2 points. The mean distance control of these participants is indicative of the
588 presence of spontaneous tropia on at least one of the 3 control measures, while
589 participants with mean distance control scores of 2 to <3 points had a phoria on one or
590 more of the control measures.

591

592 If there is no evidence of a treatment effect in the subgroup of participants with mean
593 distance control scores at baseline of 2 to <3 points (from Section 4.2.1), the distance
594 control primary analysis (Section 2, excluding sensitivity analysis) and secondary
595 analysis (Section 2.3) will be repeated in exploratory analyses limited to the cohort of
596 participants with baseline distance control of 3 to 5 points. This will be done at both the
597 12-month and 18-month time points.

598

599 [Note: this is included in the SAP only because it appeared in the Protocol. It is
600 recognized that in the event this analysis is carried out as specified, strict control over the
601 type I error rate will have been lost.]

602

603

604 **4.3 Safety Analyses**

605

606 **4.3.1 Refractive Error at 12 and 18 Months**

607 The proportion of participants with >1 D increase in myopia or in hyperopia from
608 baseline to 12 months and from baseline to 18 months will be tabulated separately by
609 direction of change (myopic or hyperopic), and treatment group, for refractive error as
610 measured by subjective refraction or retinoscopy and also for refractive error as measured
611 by autorefraction. The risk ratio for myopia progression of >1 D will be calculated for the

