724 **5.2.1. Principles to be Followed in Primary Analysis**

725 Model assumptions for the ANCOVA will be checked as described in Section 2.1.1,
726 including linearity of baseline refractive error, normal distribution, and equal variance
727 across treatment groups. If baseline refractive error was included as a continuous variable
728 in the analysis from Section 2.1, it will be included as a continuous variable in this model
729 as well; otherwise, it will be categorized.

730
731 There will be no imputation for missing data; however, baseline characteristics of
732 participants with and without follow up will be tabulated at each time point. In the event
733 there is a clinically relevant imbalance between those with and without follow up, a
734 propensity score-weighted analysis will be performed as a sensitivity analysis.

735
736 The primary analysis will follow a modified intention-to-treat principle, with all
737 participants analyzed according to their randomized treatment group. To be included in
738 the analysis, the 24-month visit must be completed no earlier than 630 days (≥ 21
739 months) and no later than 899 days (< 30 months) after randomization. If the 24-month
740 visit is not completed within this analysis window, the 18-month visit data will be used
741 instead (if available and if within 24-month window). The 36-month visit must be
742 completed no earlier than 900 days (≥ 30 months) and no later than 1440 days (≤ 48
743 months) after randomization.

744
745 As a sensitivity analysis, the primary analysis will be repeated but limited to participants
746 who completed each visit within the protocol window of +/- 3 months.

747 A separate sensitivity analysis will repeat the primary analysis but be limited to
748 participants who were not treatment crossovers at any point in the study.

749
750
751
752
753
754
755
756
757
758
759
760
761
762
763
764
765
766
767
768
769
770
771
772
773
774
775
776
777
778
779
780
781
782
783
784
785
786
787
788
789
790
791
792
793
794
795

5.3.Secondary Analysis—Comparison of Axial Length and Other Biometric Measurements Between Treatment Groups at 24 and 36 Months

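### Extension refractive error is analysed without imputation, and the only visible check for selective return is triggered by baseline imbalance, which may not show return related to 12-month myopic change

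*SAP*

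**What the plan says.** **Extension analysis (SAP 5.2.1).** On missing data: "There will be no imputation for missing data; however, baseline characteristics of" participants with and without follow-up are tabulated at each time point. The response is conditional. If "there is a clinically relevant imbalance between those with and without follow up, a" propensity-weighted sensitivity analysis is done. No threshold is given, the table is not said to be by arm, and the propensity covariates are not named. The other two sensitivity analyses (visits inside the protocol window; no crossovers) restrict the sample further and do not address non-return.

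There is one exception to using only the scheduled visit. If the 24-month "visit is not completed within this analysis window, the 18-month visit data will be used" in its place, provided it falls inside the 24-month window. Nothing similar is given for 36 months.

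**Model and entry (Protocol Amendment II, Change #6).** The comparison is an ANCOVA adjusted for baseline spherical equivalent. All enrolled children are invited, but participation needs a new consent from parents who choose to continue.

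**Refraction already collected.** Protocol 3.4: "A cycloplegic refraction will be performed at the 12-month and 18-month visits". The 18-month refraction was added only by Amendment II, so children seen earlier lack it. The SAP uses the 12-month value elsewhere. The model in 4.1.9 "adjusts for baseline refractive error and baseline age. The latter was added as a post-hoc" factor, and 4.3.1 tabulates: "The proportion of participants with >1 D increase in myopia or in hyperopia from" baseline to 12 and to 18 months.

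**Method used for distance control (SAP 2.1.9).** There, "imputation will be performed separately by treatment group to account for potential" interaction between arm and the follow-up scores.

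The opening of SAP section 5, before 5.2.1, was not in the text available to me. What follows is confined to 5.2.1 and the protocol's extension section.

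**The concern.** The extension's sole stated objective is to compare long-term refractive error between the arms. A baseline-adjusted complete-case ANCOVA is valid only if, within arm and given baseline refraction, return is unrelated to later refraction. Return that depends on myopic change seen by 12 months would break this.

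The setting makes that possible. Re-consent takes place at a 12-, 15- or 18-month visit or at another time, and families active in the full-treatment or weaning phases were to be told of the myopia finding. Change of more than 1.00 D by 12 months was "17% in the overminus group (29 of 168); and 2% in the non-overminus group (3 of 146" children. With distributions this far apart, even one common return rule selects differently in the two arms.

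The planned safeguard examines baseline characteristics. A family's reaction to 12-month change need not leave a visible mark there, so the trigger could stay silent while the estimate moves.

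**Working it through.** **1. The plan's own figures.** 29/168 = 17.3% and 3/146 = 2.1%, as stated. The difference in mean 12-month change is -0.42 - (-0.05) = -0.37 D. The protocol prints 0.39 D without saying whether it is adjusted; I use -0.37 D.

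**2. The 18-month substitution is narrow.** An on-time 18-month visit ends at 19 months, or 19 × 30 = 570 days on the SAP's 30-day month. The 24-month window opens at day 630, so only a late 18-month visit can stand in.

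**3. How many 12-month refractions could exist.** 168 + 146 + 37 visits still due = 351, and 351/384 = 0.914. This is approximate: the counts come from slightly different dates and 384 is the planned sample size.

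**4. SD of 12-month change (not given; inferred under normality).**
- Overminus: (1.00 - 0.42)/z = 0.58/0.944 = 0.61 D.
- Non-overminus: (1.00 - 0.05)/z = 0.95/2.043 = 0.47 D.
- The second value rests on 3 events. The exact 95% interval for 3/146 is 0.4% to 5.9%, which gives SDs from 0.36 to 0.61 D.

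**5. A case that can be checked by hand.** Assume children with more than 1 D progression return at 50% and the others at 75%.
- Overminus: share of progressors among returners = 0.173 × 0.50/(0.173 × 0.50 + 0.827 × 0.75) = 0.122. Truncated-normal means are -1.33 D (progressors) and -0.23 D (others). Returner mean = 0.122 × (-1.33) + 0.878 × (-0.23) = -0.364 D.
- Non-overminus: share 0.0138, means -1.17 and -0.0265 D. Returner mean = -0.042 D.
- Difference among returners: -0.322 D, which is 0.05 D (13%) closer to zero than -0.37 D.

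**6. A graded return rule, the same in both arms.** Probability of return = 0.914 × expit(a + b × 12-month change), with b = ±ln 2 or ±ln 3 per dioptre and a set so that 60% or 75% of all randomised children return. Assume the 12-month difference persists to 36 months and later change is unrelated to return. The returners' difference is then the difference between arms in E[change | return], found by numerical integration:

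| SD overminus / non-overminus (D) | Progressors return less | Progressors return more |
|---|---|---|
| 0.61 / 0.47 | -0.343 to -0.291 (7-21% smaller) | -0.383 to -0.399 (3-8% larger) |
| 0.61 / 0.36 | -0.333 to -0.264 (10-29% smaller) | -0.394 to -0.433 (7-17% larger) |
| 0.61 / 0.61 | -0.361 to -0.339 (2-8% smaller) | the same |
| 0.54 / 0.54 | -0.363 to -0.345 (2-7% smaller) | the same |

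Letting change depend on baseline refraction (0.15 D per D in overminus, 0.3 times that in non-overminus) gives about 1-9% with equal SDs of 0.61 D.

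**7. Why the SDs matter.** To first order each arm's mean moves by b × (1 - p) × SD², where p is return among children with a 12-month refraction. At 60% return, p = 0.60/0.914 = 0.656. The difference moves by 1.099 × 0.344 × (0.61² - 0.47²), about 0.06 D with unrounded SDs, and by nothing when the SDs are equal. The smaller remaining shift, toward zero, arises because the arms then return at different rates.

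**8. What the trigger would see.** In the strongest scenarios (60% return, 3-fold odds), returners and non-returners differ by at most about 0.13 SD in baseline refraction but by about 0.6 SD in 12-month change. Under a 50% versus 75% rule like step 5, weighting on baseline refraction left the estimate at -0.31 to -0.32 D; using 12-month refraction recovered -0.37 D. That recovery is by construction, since the variable driving return is in the model.

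**The case against.** **The plan is not silent on non-return.** It tabulates follow-up status at each time point and commits to weighting if imbalance appears. The covariates are unnamed, so 12-month refraction could enter the weights. This stands: a reader might infer that the SAP excludes the 12-month value, and it does not. What remains is the trigger, which as written follows a table of baseline characteristics.

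**There is no evidence of selective return.** Every enrolled child is invited, visits are compensated, spectacles are provided at the first extension visit, and retention calls may be made. This also stands. A reader might infer that the extension estimate is biased; the documents show only a gap in protection.

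**The percentages are fragile.** They rest on assumed retention, odds and persistence, and on SDs inferred from one tail count per arm. A reader might take from the first row of the table that the excess is overstated when progressors return more. With equal SDs it is understated whichever way they return, so no direction can be stated in advance. The assumption that children without a 12-month refraction never return also sits awkwardly with inviting everyone. Without it (0.914 replaced by 1) the extreme cases become 32% smaller and 20% larger.

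**Arm-specific selection would do more.** That is a tempting stronger case, but Protocol 3.3 masks families to assignment and nothing in the documents indicates that return differs by arm.

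**Observed data is the SAP's rule for refractive error (SAP 4).** True, which is why the proposal sits beside the planned analysis and does not replace it.

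**Conclusion.** The point holds as a gap in the sensitivity analysis, not as a demonstrated bias. If return depends on 12-month change, the complete-case ANCOVA is biased, and a baseline table may not show it.

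Under the assumptions above (60-75% return, 2-3 fold odds per dioptre, one rule for both arms, true difference -0.37 D), the shift runs from about 1% to about 30%, or under 0.01 D to about 0.1 D. With equal SDs it is about 1-9% toward zero; with a smaller non-overminus SD it can go either way. These are illustrations, not bounds, because the documents give neither the SDs nor extension retention. If less of the 12-month difference persists, the shift in dioptres is smaller too.

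Every scenario in the table keeps a negative difference (-0.26 to -0.43 D), so the size of the myopia excess is affected more than its direction. This is an improvement worth considering; it does not invalidate the planned analysis.

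**What to change.** In SAP 5.2.1:

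1. Tabulate follow-up status at 24 and 36 months by 12-month refraction and by change from baseline to 12 months, within arm.
2. Add one sensitivity analysis of 24- and 36-month refractive error that is run whatever the tables show. It should use baseline and 12-month refraction, age, and 18- and 24-month refraction where measured. Either multiple imputation within arm, as in SAP 2.1.9, or propensity weighting that includes 12-month refraction would serve. Report it beside the complete-case ANCOVA.

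The cost is a little more analysis on data mostly already collected, and a sentence explaining the departure from the observed-data approach if imputation is chosen. The added analysis assumes data are missing at random. It does not cover return that depends on progression after the last observed refraction.
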